36.	Partial Waiver of Consent for Screening/Recruitment	25
37.	Partial Waiver of HIPAA Authorization for Screening/Recruitment.....	26
38.	Waiver of Documentation of Consent	26
39.	Alteration of Consent.....	27
40.	Full Waiver of Consent/Parental Permission.....	28
41.	Full Waiver of Consent/Parental Permission (Public Benefit or Service Programs)	
	29	
42.	Full Waiver of HIPAA Authorization (Checklist).....	29
43.	Other Waiver Types (Checklist).....	30

44.	Vulnerable Populations (Checklist).....	30
45.	Medical Devices (Checklist).....	36
46.	Export Control (Checklist)	37
47.	Data Transfer/Sharing (Checklist).....	37
48.	Specimen Transfer/Sharing (Checklist).....	38

1. Objectives

1.1. Describe the purpose, specific aims, or objectives.

Our long-term goal is to develop a mindfulness-based intervention (MBI) program that significantly decreases stress/burnout and increases belongingness and connectedness among nurse faculty and staff. The overall objective of this pilot project, which is the next step in toward achievement of our long-term goal, is to examine the feasibility and preliminary efficacy of MBIs as an intervention for University of New Mexico (UNM) Health Sciences Center (HSC) nurse faculty and staff. Our central hypothesis is that this MBI intervention will improve the psychosocial outcomes (sense of belonging) and physiological outcomes (HRV) among HSC nurse faculty and staff. To test our central hypothesis and attain the overall objective, we will pursue the following specific aims:

Aim 1. To evaluate the feasibility and acceptability of MBIs (meditation or yoga) for HSC nurse faculty and staff. Acceptability will be assessed qualitatively from analyses of interviews with participants. Feasibility will be assessed as rates of recruitment, retention, and adherence to the MBI (% training sessions attended).

Aim 2. To evaluate the preliminary effect of MBI (meditation; yoga) in HSC nurse faculty and staff on: psycho-social outcomes (burnout; sense of belonging, stress, anxiety) and physiological outcomes (HRV evaluated by wearable electronics). We hypothesize that: a) psycho-social outcomes will improve post-intervention and b) physiologic measures (HRV) will improve post intervention compared to preintervention.

1.2. State the hypotheses to be tested.

Our central hypothesis is that this MBI intervention will improve the psychosocial outcomes (sense of belonging) and physiological outcomes (HRV) among HSC nurse faculty and staff.

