Physiologic measures: inter-beat-interval will be collected via a Garmin Vivosmart5® device. This device has been shown to produce reliable heart rate data with the mean absolute percentage error below the designated acceptable 10% threshold.³¹ Each participant will receive training for use of the sensor and written instructions will be provided for future reference. Participants will wear the device on their non-dominant hand in their daily environment every day for six weeks. Daily reminders to wear the device and to check the battery level will be delivered via the mEMA to increase compliance with the protocol.

HRV outcome measures: Garmin Vivosmart5® uses optical technology in which a series of lights emitted by photoplethysmography (PPG) sensors against the skin illuminate capillaries to detect changes in blood volume and providing heart rate data in real time.³¹ Raw data is collected from the device and sent to the phone via Bluetooth. Using the pulse to pulse (P-P) interval, inter-beat-interval (IBI) is derived via Ilumivu software. HR epochs of five-minute intervals immediately preceding and corresponding to each mEMA survey will be selected for analysis. Time and frequency domain analysis will be performed by Ilumivu using proprietary software. **Time Domain measures:** Time domain measures are based on the time difference between easily detectable QRS complexes.

Using PPG technology, these measures are derived from the P-P interval (distance in milliseconds between each P). Simple time domain measures (standard deviation of P-P interval, mean HR) will be calculated. Frequency domain measures estimate frequency spectrum. The general bands are low frequency (LF; 0.04–0.15 Hz) and high frequency (HF; 0.15–0.40 Hz). Low frequency measures, high frequency measures, and LF/HF ratio of HRV will be computed.³²

Long-term HRV, 24 hour time windows, will be determined by dividing the 24 hour time period into consecutive 5 minute epochs and averaging the individual values of the HRV metrics to obtain the mean of the value within the 24 hour time window.^{32,33} Five-minute heart rate epochs immediately following completion of each mEMA survey will also be selected for analysis.^{20,34} Between subject variability, in which relatively stable variation is compared between individuals, and within-subject (WS) variability, in which variation within the same individual across time will be examined.

12.4. Indicate what study activities happen when and where.

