For each yoga class, the instructor will lead the student through a series of yoga poses. Class will begin with centering and breathwork (pranayama) for 5-10 minutes. This will be followed by a series of warm-up poses (~5-10 minutes). After the warm-up sequence, students will flow through traditional sun salutations (~10-15 minutes). This will be followed by a series of standing poses (~ 15 minutes). Students will then be guided to flow through a series of cool-down poses on the floor (~10 minutes). Class will conclude with traditional Savasana during which affirmations or meditation are provided (~5-10 minutes).

Treatment fidelity:

Delivery: Standard treatment manuals and checklists have been developed. To ensure that the interventions are delivered as intended, yoga instructors will complete standardized checklists after each in-person session.³⁹ In addition, we will select one yoga session every 2 weeks for rating by trained research personnel. The PI and interventionists will meet to discuss results and problem solve. We will track participant's completion of study components using summary sheets for each visit. Participants will log attendance at intervention sessions using the mEMA app.

Post-intervention session: During the post-intervention assessment session, participants will be administered a structured questionnaire with a research team member via the secure REDCap system. Self-report questionnaires will be completed: 1) Sense of Belonging Scale (SBS); 2) Mindfulness Attention Awareness Scale (MASS) 15-item; 3) Generalized Anxiety Disorder-7 (GAD-7); 4) NIH toolbox measure of perceived stress. Participants will complete semi-structured (See Attachment G) interviews to help us collect data pertaining to the MBIs and delivery preferences. Interview responses will be transcribed in the REDCap system. These data will be used to adjust the content and format of the intervention based on feedback from participants who are our intended users.

13. Data Analysis

13.1. Describe the data analysis plan, including any statistical procedures.

Consistent with the scope of pilot projects, the proposed study will allow us to examine barriers to successful completion of the study, evaluation of acceptability of methods to participants, and estimates for future power analysis for a subsequent NIH R01 application. Numerical and graphical summaries will be computed for all measurements.

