Aim 1: To assess precision of estimates, 95% confidence intervals will be calculated for rates of recruitment into study, retention to end of study, and participants completing all training sessions. Overall adherence will also be described by calculating the mean and standard deviation of the number of completed training sessions per participant. Qualitative Analyses: Qualitative descriptive analysis⁴⁰ will be used to create a comprehensive summary of the acceptability of the MBI to participants. Deductive analysis will be used to determine common themes related to acceptability in the domains of affective attitude, burden, ethicality, intervention coherence, opportunity costs, perceived effectiveness, and self-efficacy.⁴¹ Interview responses will be reviewed by two members of the research team to identify themes. Themes and preliminary interpretations will be regularly presented to the larger research team to resolve any discrepancies or disagreements and check for alternative interpretations.

Aim 2: Participant characteristics and baseline survey responses will be described using means and standard deviations (SD) for continuous variables and number (percentage) for categorical variables. Continuous intervention outcomes will be described using means and standard deviations and, due to sample size, difference scores from baseline for intervention outcomes will be compared between groups using non-parametric statistical tests. Cohen's d, as a descriptive statistic, will be used as an effect size measure to quantify the extent of within group and between group differences in means over time.⁴² Long-term HRV (time domain and frequency domain measures derived for each 5 minute epoch within a 24 hour period will be averaged) measures will be compared between meditation and yoga groups by t-test. EMA and HRV data will be merged into a single dataset, matching upon timestamp.

Five-minute heart rate epochs immediately following completion of each mEMA survey will be selected for analysis.^{20,34}

13.2. Provide a power analysis, if applicable.

14. Provisions to Monitor the Data to Ensure the Safety of Subjects

This section is required when research involves more than Minimal Risk to subjects. Describe:

N/A – The PI believes this study constitutes no more than minimal risk for potential participants. Therefore, a Data and Safety Monitoring Plan is not required.

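### Aim 2 hypothesises pre-to-post improvement, but both tests in 13.1 compare meditation with yoga, and no interval, paired analysis or both-arm estimate of change is named

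*Combined protocol and SAP*

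**What the plan says.** **Hypotheses.** Section 1.1, Aim 2, expects that "psycho-social outcomes will improve post-intervention and b) physiologic measures (HRV) will improve post intervention compared to preintervention". Section 1.2 likewise speaks of improvement. Neither says that one arm should do better than the other.

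**Tests.** Section 13.1, Aim 2, names two inferential procedures. For outcomes generally, "difference scores from baseline for intervention outcomes will be compared between groups using non-parametric statistical tests". For long-term HRV, the "measures will be compared between meditation and yoga groups by t-test"; that t-test is not described as a test of change from baseline.

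**What pre-to-post change does receive.** Section 13.1 plans means and SDs, and it opens with a general commitment: "Numerical and graphical summaries will be computed for all measurements". It also plans Cohen's d, which "as a descriptive statistic, will be used as an effect size measure to quantify the extent of within group and between group differences". Section 12.3 adds, for HRV, "within-subject (WS) variability, in which variation within the same individual across time will be examined", without an estimator or a pre-post contrast.

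**Intervals.** These appear for Aim 1 only: "95% confidence intervals will be calculated for rates of recruitment into study, retention to end of study", and for completion of all training sessions.

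**Purpose and sample size.** Section 13.1 says the pilot is to give "estimates for future power analysis for a subsequent NIH R01 application". Section 5.3 and the recruitment-feasibility paragraph of section 9 justify 30 participants (per cohort, in section 9) by a medium-sized difference between two groups. Section 7.1 makes feasibility and acceptability primary for the study, and sense of belonging primary among the psychosocial outcomes.

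**The concern.** The hypothesis and the tests concern different quantities. The hypothesis is about mean change within people. The tests are about the difference in change, or in HRV level, between two active programmes. Two equally helpful programmes and two equally useless ones look the same to a between-arm test. A non-significant comparison could be taken as a sign of no improvement, and a significant one would not show that either arm improved.

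The quantity Aim 2 asks about is left as a point estimate. A pilot that feeds a later power calculation should show how uncertain its estimates are. The plan accepts this for the Aim 1 rates but does not carry it over to Aim 2.

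**Working it through.** **1. The plan's own figure.** The sample size of 30 is a pilot convention. No alpha, power, SD or numerical effect size is given, and 13.2 holds only the template prompt, so there is no calculation to reproduce.

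**2. Inputs.** From the documents: 15 per arm per cohort (12.2) and at most 60 participants in two cohorts (5.2). Hence n=15 is one arm in one cohort, n=30 is one arm at full enrolment or one cohort pooled, and N=60 is everyone. My assumptions: normal, independent change scores, the SD of change as the unit, and two-sided 5%.

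**3. What the between-arm test sees.** Let the mean changes be m1 and m2. The planned comparison tests m1 − m2 = 0, while Aim 2 concerns m1 > 0 and m2 > 0. If m1 = m2, the null hypothesis of the planned test is true whatever their size, so it rejects at its type I error rate. This holds by construction. As a check, 20,000 simulated trials with both arms improving by an assumed 0.5 SD gave:

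| Per arm | Mann-Whitney between arms rejects | Paired t over both arms rejects |
|---|---|---|
| 15 | 4.3% | 75% |
| 30 | 4.7% | 97% |

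**4. Precision of mean change.** Half-width of the 95% CI = t(0.975, n−1)/√n.
- n=15: 2.145/3.873 = 0.55
- n=30: 2.045/5.477 = 0.37
- N=60: 2.001/7.746 = 0.26

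With an assumed 20% loss (12, 24 and 48 left), these become 0.64, 0.42 and 0.29.

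**5. The same uncertainty on the Cohen's d scale.** Take an observed d of 0.5, standardised by the SD of change. The observed t is 0.5√n: 1.94, 2.74 and 3.87. Inverting the noncentral t and dividing the limits by √n gives:
- n=15: −0.05 to 1.03
- n=30: 0.12 to 0.88
- N=60: 0.23 to 0.77

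A single arm of one cohort with d = 0.5 is therefore compatible with no change and with a very large change.

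**6. Shared classes.** Interventions are given in group sessions, so participants may not be independent. There are at most four arm-by-session groups (two arms, two six-week sessions). For four groups of 15 the design effect is 1 + 14 × ICC. The documents give no ICC. For assumed values of 0.02, 0.05 and 0.10 it is 1.28, 1.70 and 2.40. With a t reference on 3 df (3.182), the half-width at N=60 is 3.182 × √(design effect)/√60 = 0.46, 0.54 and 0.64. This only illustrates that 0.26 is a best case; four groups are too few to estimate the correlation well.

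**7. Which outcomes have data at both visits.**
- *Questionnaires.* The Sense of Belonging Scale, MAAS, GAD-7 and perceived stress are listed at baseline (12.3, 12.5) and post-intervention (12.5). MAAS is not among the Aim 2 outcomes in 1.1.
- *Burnout.* It is an Aim 2 outcome and the instrument is described in 12.3, but neither list includes it.
- *HRV.* Section 12.3 has the device worn daily for six weeks, and the intervention also lasts six weeks (12.5). No pre-intervention wear period is defined.

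**The case against.** **This is a pilot.** Feasibility and acceptability are primary and the effect is called preliminary. That stands. A reader might infer that omitting a paired test is itself an error; the documents do not support this, and a pilot may reasonably estimate without testing. But the argument favours intervals and does not explain why the only tests planned concern a different contrast.

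**Pre-to-post change is already covered.** A reader might infer that the plan does nothing for it. That is wrong: means, SDs, summaries and a within-group Cohen's d are planned, and a clear improvement would show there beside a null between-arm test. If d were standardised by the SD of change, an interval could be worked out from d and n. What remains is that the standardiser is not stated, no interval is promised and no both-arm estimate is named.

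**The between-arm contrast is part of the design.** A reader might infer that it comes from nowhere. It does not: there are two defined groups, and sections 5.3 and 9 base the sample size on a difference between two groups. The accurate statement is that the contrast has no hypothesis in Aim 2, and that section 1 disagrees with 5.3, 9 and 13.1 about the question being asked.

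**The simulated rejection rate is not evidence.** Agreed. It illustrates a logical point, and the finding depends on no number.

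**Conclusion.** The mismatch is real and worth correcting before analysis. Aim 2's pre-to-post hypotheses have descriptive output but no planned interval, paired analysis or both-arm estimate, while both named tests address meditation versus yoga. Aim 1 is unaffected, so this is a modest point and cheap to put right.

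The textual finding needs no assumption. The half-widths in step 4 rest on normal, independent change scores, and those at n=15, 30 and 60 also assume no dropout; shared classes would probably make them wider.

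Two further inferences should be avoided. A paired analysis would not show that the programmes work: there is no untreated control, so it shows change and not an effect attributable to the MBI. Nor does rewording 13.1 settle every Aim 2 outcome, because HRV has no defined pre-intervention period and burnout is missing from both assessment lists.

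**What to change.** In section 13.1:

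1. Make the main Aim 2 analysis the paired pre-to-post change in the Sense of Belonging Scale with a 95% CI, by arm and pooled over arms and both six-week sessions.
2. Report the same for GAD-7 and perceived stress as supportive results, and for MAAS, noting that it is not an Aim 2 outcome in section 1.1.
3. Give a CI with each within-group Cohen's d and state its standardiser.
4. Label meditation versus yoga as exploratory.
5. State that, without an untreated control, the result is change only, and that CIs assuming independence may be too narrow because classes are shared and there are at most four arm-by-session groups.
6. For HRV, either define a baseline window and a late window from the planned device data and report within-person change with a CI, or reword hypothesis b in section 1.1 as descriptive, with a matching edit to 1.2.
7. For burnout, reconcile the instrument description in 12.3 with the assessment lists in 12.3 and 12.5 before promising a pre-to-post estimate.

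Items 1 to 5 cost wording and a little analysis, with no new data for the four listed questionnaires. HRV needs a design decision on windows or an edit to section 1. Burnout may need the instrument added to the visits.

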Assessment of burnout: The Copenhagen Burnout Inventory is a valid and reliable, 19-item, self-report measure of burnout.²⁴ Originally designed to measure burnout in among human service workers, it includes 3 scales. The personal burnout scale has six items and measures prolonged physical and emotional exhaustion. The work-related burnout scale has seven items that measure prolonged physical and emotional exhaustion secondary to work. The third scale, client-related burnout, has six items that measure burnout related to working with clients (client may be patients, students, service recipients). Each subscale can be scored separately.²⁴ The three subscales have demonstrated good reliability and criterion related validity in a variety of samples.^{24,25}

Assessment of anxiety and stress: The Generalized Anxiety Disorder-7 screener (GAD-7) is a 7-item self-report-measure of generalized anxiety disorder.²⁶ Response categories range from 0 (*Not at all*) to 3 (*Nearly every day*). Responses are summed (range, 0 to 21) with higher scores corresponding to more severe levels of anxiety. Using a cut-off of 8, the GAD-7 has a sensitivity of 92% and specificity of 76% for diagnosis of generalized anxiety disorder.^{27,28} The NIH toolbox measure of perceived stress is a 10-item fixed form. Responses are measured on a 5-point Likert scale ranging from 1 (*Never*) to 5 (*Very Often*) with higher scores indicating higher levels of perceived stress.^{29,30}

Brief Reflective Feedback: At the end of each mindfulness session, participants will be given a card on which to write two words that embody how they are feeling right now (no

identifying information will be on the card). Participants will be asked to share their two words with the group if they feel comfortable.

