Description of Intervention Delivery

These guidelines detail the procedures used to conduct Mindful Meditation or Yoga sessions.

We will employ a quasi-experimental design to assess feasibility, acceptability, and preliminary efficacy of MBIs (meditation; yoga) to increase a sense of belonging and connectedness in academic nursing faculty and staff. We will assign 15 individuals to each condition. Across both conditions, all participants will participate in one baseline assessment/training session, 6 weeks of MBIs (participants will be required to attend 2 sessions per week), and a post-intervention assessment session. Following screening for inclusion/exclusion criteria, eligible participants will complete the **BEING Mindful** Exercise participation screening. Eligible participants will provide informed consent.

Assignment of Participants:

After informed consent is obtained, research staff will allocate individuals to meditation vs yoga on a 1:1 basis. If an individual is unable to participate in the yoga arm, they will be assigned to meditation and the next two participants will be assigned to yoga.

Retention:

To promote retention, we will reach out to participants with frequent reminders via text messages and emails.

Baseline Assessment session: During the baseline assessment session, participant characteristics will be collected. Baseline self-report questionnaires will be completed: 1) Sense of Belonging Scale (SBS); 2) Mindfulness Attention Awareness Scale (MASS) 15-item; 3) Generalized Anxiety Disorder-7 (GAD-7); 4) NIH toolbox measure of perceived stress.

Intervention Delivery:

The meditation and yoga interventions are 6-week protocols. We will offer meditation sessions 4 times per week and yoga sessions 4 times per week. We will require participants to attend two sessions per week. Attendance will be tracked via the Ilumivu platform. Participants will be requested to log attendance at each session via the app.

The meditation intervention will be led by [name] and [name]. Meditation is a practice of mental exercises designed to increase focus and cultivate a desire to relieve suffering in self and other.^{35,36} The practice dates back millennia to Buddhist and Hindu sages, but more recent work focuses on stress.³⁷ More recently, the term mindfulness has been used which means awareness, attention, and remembering.³⁷ Many religious traditions have a form of meditation based practice. This study will focus

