on two forms of meditation both of which are focused on right mindfulness: 1) zazen which is a seated meditation primarily focused on the breath, posture, and sensation without attaching judgment. This is meant to develop awareness, equanimity, and insight, and 2) kinhin which is a walking meditation which is meant to connect mindfulness in one's movement by synchronizing breath and movement. It also focuses on development of awareness, equanimity, and insight. The two activities combined help the individual to nurture a thread of mindfulness. Instructors have developed a protocol (see attachment E). to standardize the delivery of the meditation intervention. The protocol includes a description of the amount of time for each phase of the practice. The protocol also includes suggested cues and dialogue which can be expressed or paraphrased in the instructors' own words.

The yoga intervention will be led by certified, 200-hour registered yoga instructors, Drs [name], [name], and [name]. Yoga is a wholistic, multidimensional practice. There are three fundamental limbs of yoga: 1) breathwork (pranyanma), 2) physical postures with breathing techniques (asanas), and 3) meditation and visualization (Dhyana).³⁸ Yoga practice unites the mind, body and spirit leading to psychophysiological changes within the individual including improved self-regulation ability and stress response, mood, well-being, and quality of life.^{8,9,13} Yoga instructors will offer modifications and props such as blocks to ensure sessions are accessible to individuals of various abilities and minimize the risk of injury. Instructors have developed a detailed manual to standardize the delivery of the yoga intervention (see Attachment F). The manual includes photos and descriptions of how to perform the pose. The manual also includes suggested cues and dialogue which can be expressed or paraphrased in the instructors' own words. Additionally, the manual includes suggested modifications or amplifications for poses so the participant can practice to their level. This allows for personalization of the yoga flow while preserving treatment fidelity.

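### Both arms are taught in groups, but section 13.1 compares them as if participants were independent; any within-group correlation would make the arm p-values too small

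*Combined protocol and SAP*

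**What the plan says.** **Delivery.** Section 12.5 (Intervention Delivery) states: "We will offer meditation sessions 4 times per week and yoga sessions 4 times per week". Each participant must attend two a week for six weeks. Sections 12.2 and 12.5 put 15 people in each condition, allocated individually 1:1. Section 5.2 allows a second six-week round, for up to 60 people. There is thus one pool of sessions per arm per cohort, and at most two pools per arm. Two people are named to lead meditation. For yoga, "The yoga intervention will be led by certified, 200-hour registered yoga instructors", with three named.

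**Interaction.** Each session ends with a two-word written reflection. Section 12.3 (Brief Reflective Feedback) adds: "Participants will be asked to share their two words with the group if they feel comfortable".

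**Analysis.** In section 13.1 (Aim 2), "difference scores from baseline for intervention outcomes will be compared between groups using non-parametric statistical tests". The tests are not named. Long-term HRV "measures will be compared between meditation and yoga groups by t-test". "Cohen's d, as a descriptive statistic, will be used as an effect size measure", with no interval stated for it. The only confidence intervals planned are under Aim 1: "95% confidence intervals will be calculated for rates of recruitment into study", and likewise for retention and session completion. Class, instructor, cohort, ICC and design effect do not appear in the analysis plan, and the power analysis in 13.2 is blank. Section 13.1 also says that the pilot is to supply estimates for the power analysis of an R01 application.

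**The concern.** A rank test or t-test on individual change scores is valid when one participant's outcome tells you nothing about another's. People who attend the same classes, share instructors and close each session together may not meet that condition. Sense of belonging, the lead psychosocial outcome in section 7.1, measures acceptance and inclusion in a community, so a shared class experience could plausibly move it for everyone present. The argument is weaker for HRV recorded through daily life on a wrist device.

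Two things are at stake. First, a class that happened to gel, or an effective instructor, could appear as a meditation-versus-yoga difference with too small a p-value. Second, the pilot's estimates would go to the R01 without a reminder that group delivery needs a design effect.

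**Working it through.** **The plan's own figure.** Section 5.3 justifies 30 by reference to a pilot-study recommendation for medium effects. It gives no alpha, power, SD or numeric effect, so there is nothing to reproduce. It claims no particular power, so none is held against it.

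**Inputs.** From the documents: 15 per arm per cohort, up to two cohorts, four sessions a week per arm, two attended. Assumed, because the documents are silent: ICC from 0 to 0.10; two-sided alpha 0.05; and, for the interval and R01 illustrations only, d = 0.5 and 80% power.

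**Group size m.** If all 15 in an arm behave as one group, m = 15. If each person picks two of the four slots at random and keeps them, there are six possible pairs of slots. Two people share both slots with probability 1/6, one slot with probability 4/6, and none with probability 1/6. Their average correlation is ICC × (1/6 + 4/6 × 1/2) = ICC/2. The variance inflation is then 1 + 14 × ICC/2 = 1 + 7 × ICC, close to two fixed subgroups of about 7.5, where it is 1 + 6.5 × ICC. So m of about 7.5 and m = 15 serve as lower and upper cases.

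**Formulas.** DE = 1 + (m − 1) × ICC. The true SE is √DE times the naive SE. Actual type I error = 2 × [1 − Φ(1.96/√DE)].

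| m | ICC | DE | √DE | Type I error |
|---|---|---|---|---|
| 7.5 | 0.02 | 1.13 | 1.063 | 0.065 |
| 7.5 | 0.05 | 1.325 | 1.151 | 0.089 |
| 7.5 | 0.10 | 1.65 | 1.285 | 0.127 |
| 15 | 0.02 | 1.28 | 1.131 | 0.083 |
| 15 | 0.05 | 1.70 | 1.304 | 0.133 |
| 15 | 0.10 | 2.40 | 1.549 | 0.206 |

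**Simulation check.** Normal outcomes, no arm effect, 6,000 runs per setting. Cells give the false-positive rate of the Mann-Whitney test / t-test.

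| Layout | ICC 0 | ICC 0.05 | ICC 0.10 |
|---|---|---|---|
| One cohort, one group of 15 per arm | 0.047 / 0.051 | 0.124 / 0.138 | 0.204 / 0.223 |
| Two cohorts, one group of 15 per arm each | 0.044 / 0.048 | 0.126 / 0.134 | 0.199 / 0.213 |
| Two cohorts, subgroups of 7–8 | 0.048 / 0.054 | 0.083 / 0.087 | 0.119 / 0.127 |
| Two cohorts, two of four slots each | 0.048 / 0.052 | 0.085 / 0.092 | 0.124 / 0.130 |

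The second cohort does not reduce the inflation, because it adds people and groups in the same proportion.

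**Interval width.** With 30 per arm and d = 0.5, the naive 95% half-width for d is 1.96 × √(2/30 + 0.25/120) = 0.514. Multiplied by √DE, it becomes 0.55, 0.59 and 0.66 for m = 7.5 at ICC 0.02, 0.05 and 0.10, and 0.58, 0.67 and 0.80 for m = 15.

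**R01 illustration.** At d = 0.5 and 80% power the normal approximation gives 63 per arm. Multiplied by DE and rounded up, that is 72, 84 and 104 for m = 7.5, and 81, 108 and 152 for m = 15.

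**The case against.** The strongest reply is that the size of the problem is unknown and the arm comparison is not what this pilot is for. Section 7.1 makes feasibility and acceptability primary. The Aim 2 hypotheses in section 1.1 concern change from before to after, not one arm against the other, and no decision depends on an arm p-value. Delivery is standardised by a protocol or manual in both arms, and yoga sessions also have instructor checklists and periodic rating. All of that stands, and it limits the consequence to interpretation and planning. It does not remove the point: 13.1 still prespecifies between-arm tests, and 5.3 speaks of differences between two groups.

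Several stronger readings are tempting, but the documents do not support them:

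- *Each arm is a single class of 15.* No fixed class is stated; people attend two of four weekly sessions. Sections 25.1.3 and 29.1.1 also let staff attend without joining the study, so classes need not be closed trial groups. The m = 15 figures are an upper case.
- *Instructor is wholly confounded with arm.* The rosters are listed separately, but the names are removed, so overlap cannot be ruled out.
- *The plan's confidence intervals are too narrow.* None is planned for the arm comparison; the Aim 1 intervals concern feasibility rates.
- *The R01 will be undersized.* Its design is not described, and a design effect can still be added when it is planned.

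**Conclusion.** The concern holds in conditional form. The between-arm tests in 13.1 assume independence that group delivery puts in doubt, and nothing in the plan acknowledges it. If the ICC is positive, the arm p-values are too small. At assumed ICCs of 0.05 and 0.10 the nominal 5% error of the rank test is about 8–9% and 12% under mixing, and up to about 12–13% and 20% if each arm acts as one group. The t-test runs up to about two percentage points higher. At ICC 0 nothing is lost.

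A reader might infer that the arm p-values are known to be wrong. They are not: the ICC is an assumption throughout, and the case for it is better for belonging than for HRV. Nor can the pilot settle the matter, since at most two session pools per arm cannot give a usable ICC. This is a worthwhile, cheap correction to an exploratory comparison; it does not undermine the pilot's primary aim.

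**What to change.** In section 13.1:

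- (a) Label the between-arm comparison, including its p-values, descriptive, and state that the tests assume independent participants although delivery is in groups.
- (b) Report the between-arm difference with a 95% confidence interval, first unadjusted and then with its variance multiplied by 1 + (m − 1) × ICC for ICC 0.02, 0.05 and 0.10, taking m of about 7.5 and 15 as lower and upper cases.
- (c) Add class date and instructor to the attendance entry that participants already make in the app. Describe outcomes by cohort and arm, and say that an ICC cannot be reliably estimated from at most two session pools per arm.
- (d) If the R01 also uses group delivery, carry an assumed ICC range, not a pilot estimate, into its power calculation.

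The cost is a few sentences, two fields in the attendance log and a few lines of analysis. Some of the session data may already be captured through app timestamps and the yoga instructors' checklists, but the plan does not say that attendance entries identify the class or instructor. The downside is that the arm comparison will look less precise. Design, sample size and interventions are unchanged.
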